The primary efficacy objective for this study is to evaluate the treatment effect of ocrelizumab compared with placebo on delaying the time to development of new radiologic or clinical evidence of MS.

Primary Efficacy Endpoint:

Time to development of first new radiologic (e.g., new or enlarging T2 lesions, T1 gadolinium-enhancing lesions consistent with MS) or clinical evidence of MS (i.e., neurological event resulting from CNS demyelination, as evidenced by acute or progressive clinical syndrome consistent with MS).

A detailed description of the primary endpoints and estimands are provided in Section 6.4.1.

SECONDARY OBJECTIVE(S)

Secondary Efficacy Objective

The secondary objectives for this study are to understand the treatment effect of ocrelizumab compared with placebo on clinical, neuroimaging and serum neurofilament light (NfL) biomarkers that are associated with disease activity, and with the clinical response to ocrelizumab.

Secondary Efficacy Endpoints:

Cumulative number of new or enlarging T2 lesions identified at Weeks 48, 104 and 208

Change in T2-lesion volume from Baseline to Weeks 48, 104 and 208

Cumulative number of new T1 gadolinium-enhancing lesions identified at Weeks 48, 104 and 208

Change from Baseline to Weeks 48, 104 and 208 in total brain volume

Change from Baseline to Weeks 48, 104 and 208 in total spinal cord volume

Change from Baseline to Weeks 48, 104 and 208 in serum NfL (sNfL)

Exploratory Efficacy Objectives

The exploratory objectives for this study are to evaluate inflammatory, neurodegenerative, and exploratory biomarkers of disease activity in the blood and cerebrospinal fluid (CSF) and their correlations with radiologic, clinical and patient reported outcomes.

Exploratory Efficacy Endpoints:

Change from Baseline to Weeks 48, 104 and 208 in white matter volume, gray matter volume, and thalamic volume

Change from Baseline to Weeks 48, 104 and 208 in spinal cord white and gray matter volume

Change from Baseline to Week 104 and 208 in CSF immune cell populations frequency and phenotype

Change from Baseline to Week 104 and 208 in CSF NfL levels

Percent change in the presence of CSF oligoclonal bands (OCB) from Baseline to Weeks 104 and 208

Percent change in normalization of CSF IgG index from Baseline to Weeks 104 and 208

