The Parties shall follow their own procedures for adherence to AE reporting timelines.

Each Party shall monitor and, as applicable, request feedback from the other Party regarding AE report timeliness in accordance with its own procedures. The Parties agree to provide written responses in a timely manner to inquiries from the other Party regarding AE reports received outside the agreed upon Agreement timelines. If there is any detection of trends of increasing or persistent non-compliance to transmission timelines stipulated in this Agreement, both Parties agree to conduct ad hoc or institute a regular joint meeting to address the issue.

In case of concerns related to non-compliance of processes, other than exchange timelines, with this Agreement, the Parties will jointly discuss and collaborate on

clarifying and resolving the issues causing non-compliance. Every effort will be made by the non-compliant Party to solve the non-compliance issues and inform the other Party of the corrective and preventative actions taken.

Upon justified request, given sufficient notice of no less than sixty (60) calendar days, an audit under the provisions of this Agreement can be requested by either Party. The Parties will then discuss and agree in good faith upon the audit scope, agenda and execution of the audit. The requesting Party will bear the cost of the audit.

STATISTICAL CONSIDERATIONS

Unless otherwise specified, all baseline and efficacy analyses will be based on the intend-to-treat (ITT) population (defined as all randomized patients). The safety evaluable population will include all patients who received any amount of study drug. Unless otherwise specified, all baseline and efficacy analyses will use the ITT population as assigned by randomization. Safety analyses will be performed by treatment received.

The primary analysis will occur when the last randomized patient has reached 4 years and the specified number of new radiological or clinical evidence of MS has accrued as specified in Section 3.1.

All statistical hypotheses for the primary and secondary endpoints and treatment comparisons will be tested at the 5% significance level ($\alpha = 0.05$) against two-sided alternatives unless otherwise specified. The SAP will contain full details of the statistical analyses specified for this protocol.

DETERMINATION OF SAMPLE SIZE

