The purpose of this study is estimation and hypothesis testing regarding the effect of ocrelizumab on the time from baseline to radiological or clinical evidence of MS relative to placebo. P-values, point- and interval estimates of the true underlying hazard ratio will be obtained.

The sample size of this trial is based on testing the null hypothesis of no difference between the control and ocrelizumab arms. This study will enroll approximately 100 patients with an expected recruitment of over 2 years. The sample size of this study is driven by the primary efficacy analysis of radiological or clinical evidence of MS and the following assumptions:

A two-group test of equal times to radiological or clinical evidence of MS

Two-sided type I error = 0.05

33% of the patients in the control arm and 20% of patients in the ocrelizumab arm having radiological or clinical evidence of MS occurring by 4 years.

A final analysis is based on approximately 21 radiological or clinical events to have 80% power 10% annual dropout rate.

SUMMARIES OF CONDUCT OF STUDY

The number of patients who enroll, discontinue, or complete the study and ocrelizumab administration will be summarized. Reasons for premature study discontinuation and treatment discontinuation will be listed and summarized. Major protocol deviations, including violations of inclusion/exclusion criteria will also be listed and summarized.

SUMMARIES OF TREATMENT GROUP COMPARABILITY

Demographic and baseline characteristics (including age, sex, body mass index), medical history, and neurological examination will be summarized using means, standard deviations, medians, and ranges for continuous variables and proportions for categorical variables, as appropriate. MS disease history (duration since MS first symptom, duration since MS diagnosis), MS disease status (MS treatment naïve or experienced) will be summarized. The baseline measures of MRI, EDSS, or other important endpoints will also be tabulated. Summaries will be presented overall and by patient cohorts.

EFFICACY ANALYSES

The primary efficacy analysis population will consist of all randomized patients, with patients grouped according to their assigned treatment (i.e., the ITT population). All statistical hypotheses for the primary and secondary endpoints and treatment comparisons will be tested at the 5% significance level against two-sided alternative unless otherwise specified.

Primary Efficacy Endpoint

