Population-level-summary estimator: The hazard ratio from a stratified Cox-proportional hazards model will be used. The stratified log-rank p-value will be used to test for statistical significance. Both will be stratified by the factors specified (see Section 4.2.1) for randomization.

Handling of missing data:

Withdrawal from study: a patient will be censored at the time of withdrawal from study.

Missing assessments at scheduled visits prior to last assessment: Missing data at scheduled visits prior to last assessment will not be imputed.

Secondary Efficacy Endpoints

The secondary endpoints for this study are to evaluate the efficacy and impact of ocrelizumab compared with placebo on the basis of the endpoints as described in Section 2.2.1 and biomarkers of disease activity and neuroaxonal damage in peripheral blood.

Each change from baseline for continuous secondary endpoints will be tested and analyzed using a stratified mixed-effects model for repeated measures (MMRM)

assuming missing at random (MAR). Sensitivity analyses will be conducted to assess the validity of this assumption,

For MRI related count endpoints (cumulative number of T2 lesions and T1 gadolinium-enhancing lesions), generalized linear methods appropriate for count data will be used depending on the distribution of the counts, e.g., a stratified negative binomial regression model.

Estimands for the Secondary Analyses

The estimands for the remaining secondary endpoints will have the same population and handling of missing data attributes as for the primary analysis.

Exploratory Efficacy Endpoints

Analyses on exploratory efficacy endpoints will be performed as data allows.

Exploratory efficacy endpoints are listed in Section 2.2.2. Further details will be described in the SAP.

SAFETY ANALYSES

The safety analysis population will consist of all randomized patients who received at least one dose of study drug, with patients grouped according to treatment received.

Safety will be assessed through summaries of exposure to study treatment, adverse events, changes in laboratory test results, and changes in vital signs and ECGs. Study treatment exposure (such as treatment duration, total dose received, and number of cycles and dose modifications) will be summarized with descriptive statistics.

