All verbatim adverse event terms will be mapped to MedDRA thesaurus terms, and adverse event severity will be graded according to CTCAE v5.0 grade. All adverse events, serious adverse events, adverse events leading to death, adverse events of special interest, and adverse events leading to study treatment discontinuation that occur on or after the first dose of study treatment (i.e., treatment-emergent adverse events) will be summarized by mapped term, appropriate thesaurus level, and severity grade. For events of varying severity, the highest grade will be used in the summaries. Deaths and cause of death will be summarized.

Associated laboratory parameters, such as hepatic function, renal function, and hematology values, will be grouped and presented together. Marked abnormalities will also be flagged.

BIOMARKER ANALYSES

Biomarkers will be assessed at baseline (screening) and subsequent time points following administration of ocrelizumab or placebo. Biomarkers levels at baseline or over time may be compared with efficacy or safety measurements to assess prognostic or

predictive properties. Biomarkers may also be analyzed over time as absolute values and/or percent change relative to baseline over time, and may be compared with efficacy, other biomarkers, or safety measurements.

INTERIM ANALYSES

The iDMC will review interim analyses as specified in the iDMC Charter. Interim analyses will be conducted by the unblinded statistician(s) and will focus on recruitment/enrollment, study conduct and safety.

No formal interim analyses for futility or efficacy are planned. However, the aggregate rate of the primary outcome will be monitored throughout the study to assure a sufficient number of events. The following scenario may trigger an interim look for futility.

If we are not on target to reach the hypothesized number of events (in the blinded dataset) by the end of the follow-up period, we will assess whether an extension to follow-up is fiscally feasible. If follow-up is feasible, a non-binding futility analysis using an alpha-spending function will be conducted to determine whether it is worth extending follow-up.

Similarly, we will monitor the current trend of treatment in this patient population. The following scenario may trigger an interim look for efficacy if applicable.

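### The model for the continuous secondary endpoints names neither the endpoint's own baseline value as a covariate nor an analysis scale for serum NfL and T2 lesion volume; followed as written, it loses precision

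*Combined protocol and SAP*

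**What the plan says.** Section 2.2.1 lists four continuous secondary endpoints at Weeks 48, 104 and 208: T2 lesion volume, total brain volume, total spinal cord volume and serum NfL. Two of them read "Change in T2-lesion volume from Baseline to Weeks 48, 104 and 208" and "Change from Baseline to Weeks 48, 104 and 208 in serum NfL (sNfL"). Neither entry gives a scale.

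The Secondary Efficacy Endpoints section of Statistical Considerations gives one model for all four: "Each change from baseline for continuous secondary endpoints will be tested and analyzed using a stratified mixed-effects model for repeated measures (MMRM"). On missing data, the model is fitted "assuming missing at random (MAR). Sensitivity analyses will be conducted to assess the validity of this assumption". The section lists no fixed effects, baseline covariate, covariance structure or transformation. It does not define the stratification, but the primary analysis uses the two randomization factors of Section 4.2.1 (spinal cord lesions and CSF oligoclonal bands), and the same is presumably meant here. Neither factor is the baseline value of a secondary endpoint.

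The endpoints are formally tested: "All statistical hypotheses for the primary and secondary endpoints and treatment comparisons will be tested at the 5% significance level against two-sided alternative". Two other sentences bear on the point. Biomarker Analyses allows a choice of scale: "Biomarkers may also be analyzed over time as absolute values and/or percent change relative to baseline over time". The opening of Statistical Considerations defers detail: "The SAP will contain full details of the statistical analyses specified for this protocol". The supplied combined document has no further section that gives it.

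**The concern.** A change score removes the baseline with a fixed coefficient of one. Unless baseline and follow-up are almost perfectly correlated, that coefficient is too large, and the excess adds noise to the treatment comparison. A model with baseline as a covariate estimates the coefficient, and in large samples its variance is never larger than that of the change score.

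Scale is a second issue. Concentrations and lesion volumes are positive and often right-skewed. If they are, a few large values dominate a comparison of absolute changes.

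With about 100 patients and 10% annual dropout, the later visits are thin and these comparisons can use the precision. Because the endpoints are tested at 5%, unstated covariates and scale also leave a choice open that should be closed before treatment codes are known.

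**Working it through.** **Plan's own figure.** None exists for this point. The documents give no power, SD, correlation or distribution for any secondary endpoint; their one power figure concerns the primary endpoint. Correlations, log-SDs and effect sizes below are therefore assumptions, shown over a range.

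**Inputs from the documents.** About 100 patients, 1:1, so 50 per arm; two-sided 5%; 10% annual dropout (Determination of Sample Size). If dropout compounds, 50 × 0.9^(48/52) ≈ 45, 50 × 0.9² = 40.5 and 50 × 0.9⁴ ≈ 33 per arm remain at Weeks 48, 104 and 208.

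**Step 1: baseline adjustment.** Take one visit, equal SD σ at baseline and follow-up, and correlation r.

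- Change score, per-patient variance: 2σ²(1−r)
- Baseline-adjusted: σ²(1−r²)
- Ratio: (1−r²)/[2(1−r)] = (1+r)/2, a reduction of (1−r)/2

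The smallest difference detectable with 80% power is (1.960 + 0.842) × √(2V/n), where V is the variance above in units of σ². At n = 40.5 and r = 0.5, this is 2.802 × √(2 × 1/40.5) = 0.62 SD for the change score and 2.802 × √(2 × 0.75/40.5) = 0.54 SD adjusted. The last column gives the adjusted power for a contrast that has 80% power unadjusted, Φ(2.802/√[(1+r)/2] − 1.960).

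| r | Variance cut | Detectable difference, Week 104: change → adjusted | 80% becomes |
|---|---|---|---|
| 0.5 | 25% | 0.62 → 0.54 | 90% |
| 0.7 | 15% | 0.48 → 0.45 | 86% |
| 0.8 | 10% | 0.39 → 0.37 | 84% |
| 0.9 | 5% | 0.278 → 0.271 | 82% |
| 0.95 | 2.5% | 0.197 → 0.194 | 81% |

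The gain differs by endpoint. It is material at r of 0.5–0.7, which could be assumed for serum NfL. It is small at 0.9–0.95, which could be assumed for T2, brain and cord volumes.

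**Step 2: log scale.** Assume log-normal values with log-SD s, log-scale correlation r and a small multiplicative treatment effect. The raw change score has variance proportional to 2(exp(s²) − exp(rs²)), and the log change has variance 2s²(1−r). The efficiency of log relative to raw is

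(exp(s²) − exp(rs²)) / (s²(1−r)).

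At r = 0.7:

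- s = 0.5: (exp(0.25) − exp(0.175))/(0.25 × 0.3) = 0.0928/0.075 = 1.24, a gain of 24%
- s = 0.7: (exp(0.49) − exp(0.343))/(0.49 × 0.3) = 0.2231/0.147 = 1.52, a gain of 52%

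The simpler ratio (exp(s²) − 1)/s² gives 14% and 29%. It describes follow-up values alone, so it does not apply to a change score.

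**Step 3: both together.** The two gains should not simply be multiplied. Simulated power under log-normal data (6,000 runs per case):

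| Case | n per arm | Raw change | Raw + baseline | Log change | Log + baseline |
|---|---|---|---|---|---|
| s 0.5, r 0.7, 20% reduction | 40 | 58% | 71% | 74% | 80% |
| same | 33 | 50% | 62% | 64% | 70% |
| s 1.0, r 0.95, 15% reduction | 40 | 31% | 36% | 62% | 62% |
| same | 33 | 26% | 31% | 55% | 55% |

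In the first pattern both changes help. In the second, which could be assumed for a skewed and stable lesion volume, nearly all of the gain comes from the scale.

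**The case against.** **Silence is not exclusion.** The model sentence names a model class and lists no terms, not even treatment or visit. A reader might infer that the plan deliberately leaves baseline out and fixes a raw scale. The documents do not support that: detail is deferred to an SAP, and Biomarker Analyses permits percent change, which can cover serum NfL. This stands. What remains is that the one stated model, applied as written, has no baseline term, and nothing supplied adds one. The percent-change wording is optional and does not settle the scale.

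**No bias follows.** A reader might also infer that chance baseline imbalance biases the result. Under randomization with complete data, the unadjusted comparison is unbiased and its standard error already reflects chance imbalance; baseline MRI measures will be tabulated in any case. With dropout, conditioning on baseline would make the missing-at-random assumption easier to defend, but no bias has been shown or sized.

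**The log scale is not free.** It replaces an absolute change with a ratio, and for T2 volume it gives a fixed absolute growth more weight in patients with little disease. It also fails at zero. This stands, which is why the log scale is only optional for T2 volume. Zeros should be rare at entry: dissemination in space needs lesions in at least two of four areas, only one of which is the cord, so each patient should have a brain T2 lesion.

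**The count models are a separate matter.** The plan leaves their form open, and nothing here supports changing their covariates.

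**Conclusion.** The point holds as a loss of precision and a gap in prespecification for the continuous secondary endpoints. The size depends on the endpoint. The baseline term saves 15–25% of variance at assumed correlations of 0.7–0.5, and 2.5–5% at 0.95–0.9. The log scale adds about 24% (log-SD 0.5) or 52% (log-SD 0.7) efficiency for change scores, if the data are log-normal with r = 0.7 and the effect is multiplicative. The formulas treat one visit at a time and ignore information shared across visits, so they are approximate.

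The practical gain is therefore mainly for serum NfL, from both changes, and possibly for T2 volume, from the scale. For brain and cord volume, the baseline term is good practice with little effect. The primary analysis is not affected.

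**What to change.** Before unblinding, state the MMRM in full: treatment-by-visit, baseline value-by-visit and the two randomization factors, for each continuous secondary endpoint.

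For serum NfL, prespecify the analysis on the log scale with log baseline as the covariate, reported as a ratio of geometric means. Do the same for T2 volume if the team prefers a relative measure, and give the reason. State a rule for zero values, and say plainly that the estimated quantity becomes relative rather than absolute change. The absolute change can still be summarized alongside.

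The cost is SAP wording and a short justification of scale. No extra data are needed, because the baseline MRI and serum measurements are already scheduled.
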